- Can the device (VAD) deliver the appropriate level of strain compared to a manometer in both a standard position and with postural modification (lying flat with leg elevation at end of strain) in healthy volunteers performing a VM?

Rationale and background

The VM is an established and internationally recommended first line treatment for SVT.¹ It causes a transient reflex physiological slowing of the heart (vagal tone) in healthy subject and can terminate attacks of SVT in patients. It is an extremely safe physical manoeuvre which mimics normal physiological responses e.g. straining at stool, child birth or when blowing up a balloon.

However, in routine clinical practice, this physical manoeuvre has a low (5-20%) rate of success for treating SVT² requiring the subsequent use of unpleasant intravenous treatments. Recent studies have shown that much better cardioversion rates approaching 50% can be achieved using a postural modification to the manoeuvre together with a controlled strain using an adapted manometer.³ Using a manometer in routine care is not practical and cannot be given to patients to use out of hospital (attacks can recur and patients can perform their own VM).

Blowing on an empty 10ml syringe has been suggested as a surrogate for the pressure required for the best VM.⁴ However, other recent studies have demonstrated syringes are unreliable in providing correct and consistent pressures during the VM strain.⁵ A prototype device has been developed based upon well-established anaesthetic breathing circuit devices which provide resistance to exhalation (positive end expiratory pressure release pop-off valves). These have been modified to provide the recommended VM strain pressure (40mmHg) resistance, are small and portable and are now ready for testing in healthy volunteers.

The device is a small plastic tube with a standard disposable mouth piece to which can be fitted a standard breathing circuit (HME) filter to allow reuse of the device and connection of a manometer to monitor the strain without risk of cross contamination of the device (see figure 1). The device's pop off valve prevents users from blowing a pressure in excess of 40mmHg and also allows a slow leak once this pressure is achieved giving audible feedback to the user and researcher that the correct pressure is being achieved. This leak also prevents use of just mouth pressure and ensures intrathoracic pressure is appropriately raised a key component of the VM.

By connecting this device to a manometer, its performance can be tested during the VM strain. As there is a normal physiological response to the VM which varies according to the degree of vagal tone, the effects of a VM using the device can also be compared to a strain using a manometer alone and with and without postural modification by assessing the fall in pulse rate during the manoeuvre.⁶

Demonstrating the device is as effective as a manometer and works with a posture modified VM in normal volunteers would support its use in routine care and enable further evaluation in patients. The device, packaged with instructions for use, would be a useful piece of equipment for use in emergency departments and by paramedics and for patients who suffer from SVT.

Aims and objectives

Aims:

- The aim of this study is to confirm the physiological effects of a modified VM and evaluate the performance of a novel Valsalva assist device in healthy volunteers

Objectives:

- To evaluate whether there is a difference in vagal tone (drop in heart rate) in healthy volunteers performing a modified VM verses a standard supine VM using the VAD.
- To evaluate whether there is a difference in vagal tone (drop in heart rate) in healthy volunteers performing a modified VM verses a standard supine VM using a manometer.
- To measure and compare peak strain pressure and duration produced using the device compared to a standard manometer in supine and modified postures

Figure 1. Valsalva Assist Device (VAD). Fitted with disposable mouth piece and filter

Research Design

We will conduct a single centre repeated measures observational study of use of the device to generate a Valsalva strain initially in a sample of healthy adult volunteers from the University of Exeter or RD&E Hospital staff, this is not related to their role within RD&E of University of Exeter, but due to convenience as the study is happening at the University of Exeter clinical research facility on the RD&E site, this will hopefully increase the likelihood of people taking part. All participants will be screened for eligibility (Figure 2) and undergo informed written consent prior to participation. If participants fail screening due to abnormal clinical readings or vital signs, the chief investigator will review them, any urgent abnormalities (very unlikely) would be reviewed by the chief investigator or delegated emergency department doctor as soon as they are discovered. Depending on the severity, if treatment is required urgently then they will be treated in the emergency department. Otherwise they will be referred back to their Gp. Potential participants will be given written information about the study at least 24 hours prior to recruitment and interested individuals invited to attend screening, recruitment and testing.

Potential participants will be invited to express an interest in taking part by responding to trial poster. These posters will be displayed in the student common room in the RILD, the medical department of St Luke's and in the ED department noticeboard. Our main target population will be medical students and medical sciences students and ED department staff; students will be directed to the trial poster at some medical student lectures. The potential participant contacts the researcher leading the practical aspects of the trial by phone or email. Respondents will be asked how they would like to receive further information (post, email, and phone) and offered an appointment at the Clinical Research Facility (CRF) for screening and written consent if eligible, at their convenience but at least 24 hours after receiving the information sheet. Given the simple, safe and quick nature of the interventions, participants will be given the choice to take part after written consent or to return on another date, whichever they would prefer, to ensure minimal visits whilst giving participants further time to consider taking part should they wish.

The VM is an extremely safe, physiological manoeuvre which is used in everyday life (eg straining at stool) and has been used in trial conditions and clinical practice many thousands of times with no serious adverse events. We will exclude participants who could conceivably be at any risk of harm from performing a VM or from use of the device.

Screening will include 12 lead ECG and physical examination including observations of pulse, oxygen saturations, respiratory rate and blood pressure. Any participants with any detected abnormalities whether they are excluded from participation or not will be informed and referred to their primary care physician as appropriate. All testing will be conducted in the clinical research facility (CRF) of the Royal Devon & Exeter Hospital, according to a strict trial protocol.

Figure 2. Inclusion and Exclusion Criteria

Inclusion Criteria:

Adult Volunteers between 18 and 60 years old from University of Exeter or RD&E Hospital staff

Sinus rhythm on initial ECG

Self-reported good health

Exclusion Criteria:

Any regular medication other than the oral contraceptive

Previous cardiovascular or respiratory disease

Any contra-indication to performing a VM strain. (Eg. Known aortic stenosis, recent myocardial infarction, glaucoma, retinopathy)

Pregnancy

Any ECG abnormality

Any contra-indication to postural modification (any reason the participant can't lie flat and have both legs lifted to 45 degrees, eg prosthetic hip)

Inability or refusal to give written consent to take part

Observations of pulse, oxygen saturations, respiratory rate or blood pressure outside the normal range. Specifically blood pressure less than 100 systolic

Caffeinated drinks within 6 hours prior to testing

The use of stimulant drugs or alcohol within 24 hours prior to testing

Test Valsalva Manoeuvres:

Participants will undergo a total of 4 VMs of the following 4 variations in random order, stratified by method of strain generation to ensure balance between the order of manometer and device use:

1. *Supine VM using manometer.* Supine Valsalva strain using a manometer visible to the participant with a target of 40mmHg for 15 seconds
2. *Supine VM using device.* Supine Valsalva strain using the device connected to manometer invisible to the participant but visible to a researcher for 15 seconds
3. *Modified VM using manometer.* Semi-recumbent (at 45 degrees) Valsalva strain using a manometer visible to the participant with a target of 40mmHg for 15 seconds followed by supine positioning and passive 45 degree leg lift immediately at the end of the strain for a further 15 seconds (the modified VM)
4. *Modified VM using device.* Semi-recumbent (at 45 degrees) Valsalva strain using the device connected to manometer invisible to the participant but visible to a researcher for 15 seconds followed by supine positioning and passive 45 degree leg lift immediately at the end of the strain for a further 15 seconds (the modified VM)

All testing will be performed on a standard hospital trolley with a manually adjustable back rest. A 45 degree angle template guide will be used to ensure consistent back rest and leg elevation angles where needed. Participant will rest for 5 minutes prior to testing to ensure they start with a resting heart rate. Participants will be given clear, standardised instructions for each manoeuvre. The strains are intuitive with feedback from the manometer or device noise and no practices will be allowed. A stop watch will be used to time strains and will be visible to participants. Participants will be instructed to stop blowing after the 15 second strain but no other encouragement or instruction will be allowed. No participant will be allowed to blow more than 50mmHg on either the manometer or device.

Blowing over 40mmHg is not likely as the manometer (with target marked) will be visible to participants when using the manometer delivered strain and the devices are set to release at pressures over 40mmHg. However as a safety measure, the researcher will ensure no participant exceeds this level during any of the VMs. In the rare event of device malfunction (ie it provides no resistance or resistance is greater than 50mmHg), the VM will be immediately abandoned and the malfunction recorded as an adverse incident. The particular manoeuvre will be restarted using a new device, only if the participant is happy to continue.

A new mouth piece and HME filter for the device and a new 92cm length of green oxygen bubble tubing, for the manometer, will be used for each participant.

There will be a three minute washout period between strains including two minutes rest after any change in posture. Continuous 3 lead ECG monitoring on a standard print enabled monitor will be used to assess heart rate during the manoeuvre. ECG rhythm strip traces would be printed for 45 seconds (15 seconds before, during and 15 seconds after each VM). They will be marked at the onset of each Valsalva strain, labelled with a code and subsequently analysed, blind to technique according to the method described by G Smith⁶:

Pre-manoevr heart rates will be determined by calculating the mean R-R interval of the 10 beats preceding each manoeuvre before converting it to heart rate in beats/minute. The lowest post manoeuvre heart rate will be determined by measuring and recording the longest R-R interval during and up to 15 seconds post manoeuvre. This will also be converted to a heart rate in beats per minute. The difference between the pre and post manoeuvre heart rate will indicate the degree of vagal tone or slowing of heart rate induced by each manoeuvre.

Peak sustained pressures achieved as observed on the manometer and duration of longest strain attempt during all VMs will be recorded on a standard report card. This will allow comparison of the different strain techniques.

Participants will be closely monitored for any adverse events. Though none are expected, if any participant feels unwell or develops any significant or persistent ECG abnormalities, the individual will be immediately withdrawn from further testing and appropriate further clinical assessment will be arranged. All adverse events will be recorded, graded and reported immediately to the CI and sponsor and reviewed by the study team.

Data Management

The data will be de-identified and stored on encrypted and password protected computers and laptops. Personal data such as name and e-mail address will be held separately. All data will be stored on University of Exeter computers with a designated University of Exeter member of staff responsible for destruction. Paper copies need to be scanned and destroyed and electronic records kept for a period of 5 years following the completion of the study, in line with University guidelines. The member of staff responsible for data storage and disposal will be the Chief Investigator ([name]) or their designated deputy from the research team at the University of Exeter.

Software

Data will be stored on Excel and analysed using STATA.

Statistical Analysis (Revised)

The heart rates measured under each of the four testing scenarios will be summarised appropriately, e.g. mean and SD, or median and IQR if necessary; it is expected that heart rate will be approximately normally distributed.

The contrasts of interest are to compare heart rate for:

1. Supine VM vs modified VM (recognising that this comparison may or may not be different according to which instrument is used – manometer or device)
2. Manometer vs device (recognising that this comparison may or may not be different according to the posture adopted – supine or modified)

The analysis will be based on mixed effects linear regression (with appropriate prior assessment of assumptions, e.g. Normality), with individual as a random effect, position (supine/modified) as a fixed effect and instrument (manometer/device) as a fixed effect. An interaction term (position x instrument) will be examined to consider whether there is any evidence of a differential effect (of device according to position, or equivalently position according to device), but will be dropped from the model if $p > 0.1$. If the interaction term is retained then comparison 1 between postures will be presented separately by device, and comparison 2 between devices will be presented separately by posture type; otherwise the two comparisons will be presented overall.

Sample size calculations are based on a simple paired t-test. There is no obvious way to determine a “smallest clinically important difference”, but we have used 4 beats per minute as a reasonably small difference, below which is unlikely to be important clinically. The SD reported in G Smith et al is about 12 (similar for individual measures and for differences between measures). With these parameters, a sample size of at least 73 participants provides 80% power at the 5% level of significance.

Project management

The programme team consists of a multidisciplinary team with complementary skills and expertise as follows:

[name] is the Chief Investigator and will lead the project and provide clinical expertise and advice.

[name] is a statistician and director of the research design service. He will advise on design and statistical aspects of the project.

[name] will run the day to day practical aspects of the study as part of her Intercalated Master by Research Project

[name] will act as academic supervisor and provide academic support to the project.

The project team will meet regularly for the duration of the study.

Dissemination

The results will be presented at UK Emergency Medicine conferences (RCEM Scientific Meeting), the National Clinical Studies Group Meeting and South West Emergency Academic Team (SWEAT) Meeting. If the results are sufficiently strong, then a paper will be written for publication in an appropriate emergency medicine journal.

Patient involvement

The initial study will be conducted in healthy student volunteers, however if the device performs as expected, there will be a need for it to be tested in a wider population and there may be an opportunity to involve patients in the design and conduct of this stage of research through the Exeter 10,000 project. We have had feedback on our information sheet from lay representatives of the Exeter 10,000, and have re-worded the information sheet in light of these comments. Should this be the case, volunteers from this scheme will be involved in designing a modified protocol and information aimed at patients. In addition, the Arrhythmia Alliance, a patient support charity, who were partners in the original research underpinning this project and can provide further help with dissemination of results or findings relevant for patients. We will also be showing actual SVT patients the device and informally be asking for patient opinions during the lifetime of the project to prepare for the next stages if the evaluation is successful in volunteers.

Timelines

Months	-2	-1	0	1	2	3	4	5	6	7	8	9	10	11
2017/18	June	July	Aug	Sept	Oct	Nov	Dec	Jan	Feb	Mar	April	May	June	July
Ethics Approval														
R&D Approval														
Trial Procedures Design														
Recruitment & Testing														
Data Analysis														
Write Up & Examination														
Project Meetings														

References

¹ Resuscitation Council (UK) Resuscitation Guidelines 2005.

<http://www.resus.org.uk/pages/guide.htm>

² Smith G, Morgans, Boyle M. Use of the valsalva manoeuvre in the prehospital setting: a review of the literature. *Emerg Med J*. 2009;26:8-10

³ Appelboam A, Reuben A, Mann C, et al; REVERT Trial Collaborators. Postural modification to the standard Valsalva manoeuvre for emergency treatment of supraventricular tachycardias (REVERT): a randomised controlled trial. *Lancet* 2015;386:1747–53.

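### Half to three quarters of device strains follow a gauge-guided manometer strain, so pooled device pressure may overstate what the device delivers to users without a gauge; pressure before any gauge exposure should be reported alongside

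*Combined protocol and SAP*

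**What the plan says.** Test Valsalva Manoeuvres gives each participant four strains in random order, two on the manometer and two on the device, "stratified by method of strain generation to ensure balance between the order of manometer and device use". The exact sequences are not listed.

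The pressure feedback differs by instrument. Manometer strains are made with the gauge in view and the 40 mmHg target marked. Item 2 describes the device condition as "Supine Valsalva strain using the device connected to manometer invisible to the participant but visible to a researcher for 15 seconds"; item 4 hides the gauge in the same way for the modified posture. Rationale and background explains that the device leaks audibly once 40 mmHg is reached and that its valve stops users going higher. On rehearsal, the text says "The strains are intuitive with feedback from the manometer or device noise and no practices will be allowed". A stopwatch is in the participant's view and participants are told when to stop. Strains are separated by three minutes.

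Research question 3 asks whether the device can deliver the appropriate strain compared with a manometer, and the third objective compares peak pressure and duration. Both are recorded for every strain. Statistical Analysis (Revised) writes a model for heart rate only, with individual, position, instrument and the position-by-instrument interaction. It has no term for strain order, and no analysis of pressure or duration is set out.

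On the setting of use, Rationale and background says: "Using a manometer in routine care is not practical and cannot be given to patients to use out of hospital".

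**The concern.** Hiding the gauge and barring practice suggest that device pressure is meant to reflect an unrehearsed user guided by the device's own cue, although the protocol does not state this reason. The crossover partly undoes it. A participant who has just held 40 mmHg for 15 seconds while watching a dial has had a rehearsal at the target pressure, and three minutes of rest is not designed to erase learning.

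Balanced order cancels a trend that affects both instruments alike. It cancels carry-over between instruments only if this is equal in both directions. There is reason to think it may not be: on the manometer the dial shows the pressure whatever came before, whereas on the device a memory of what 40 mmHg feels like could still help.

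At stake is the reading of research question 3. The intended users are largely people without a manometer. If gauge exposure raises later device pressure, the pooled device mean describes a mixture of exposed and unexposed users, and the error favours the device.

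**Working it through.** **Inputs.** From Test Valsalva Manoeuvres: two manometer (M) and two device (D) strains per participant, order balanced by instrument. From Statistical Analysis (Revised): 73 participants, 4 beats per minute, SD about 12. Assumed, because the documents give no figures: the gain in device pressure from gauge exposure, the reverse gain, and the SD of device pressure.

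**1. The plan's own figure.** The protocol says "Sample size calculations are based on a simple paired t-test" and that "a sample size of at least 73 participants provides 80% power at the 5% level of significance". With noncentrality (4/12)·√n and a two-sided 5% test, n = 72 gives 79.7% power and n = 73 gives 80.2%. The 73 is reproduced and is not in question.

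**2. Share of device strains after a gauge-guided strain.** Over the six instrument orders:

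| Order | Device strains after at least one M |
|---|---|
| MMDD | 2 of 2 |
| MDMD | 2 of 2 |
| MDDM | 2 of 2 |
| DMMD | 1 of 2 |
| DMDM | 1 of 2 |
| DDMM | 0 of 2 |

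- Unrestricted order: 8/12 = 2/3.
- Blocked (MMDD, DDMM): 2/4 = 1/2.
- Alternating (MDMD, DMDM) or mirrored (MDDM, DMMD): 3/4.

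If half the participants start on the manometer, 1/2 is the floor, since every device strain of those participants is exposed. With 73 × 2 = 146 device strains, the shares are 73, about 97 and about 110.

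**3. What balancing leaves behind.** Let a be the gain in a device strain after any manometer strain, b the gain in a manometer strain after any device strain, and s the share above (the same for both instruments under balance). Linear period effects cancel, and:

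- bias in device minus manometer = s·(a − b)
- excess of the pooled device mean over unexposed performance = s·a, whatever b is

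If b = 0, the bias is 0.50a, 0.67a or 0.75a. If b = a/2, it is 0.25a, 0.33a or 0.375a. If b = a, it is zero, but the pooled device mean is still raised by s·a.

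Illustrative excess of the pooled device mean, in mmHg:

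| Assumed a | s = 1/2 | s = 2/3 | s = 3/4 |
|---|---|---|---|
| 1 | 0.5 | 0.7 | 0.75 |
| 2 | 1.0 | 1.3 | 1.5 |
| 3 | 1.5 | 2.0 | 2.25 |

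Taking the 40 mmHg release as a ceiling, a cannot exceed the average unexposed shortfall. So a = 3 requires an unexposed mean of at most 40 − 3 = 37 mmHg.

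**4. Precision of an estimate before gauge exposure.** About half of 73 participants (36 or 37) start on the device. With one value per participant, the half-width is t(0.975, 35)·SD/√36 = 2.03·SD/6: 1.0, 1.7 and 3.4 mmHg at assumed SDs of 3, 5 and 10.

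**5. Why an exposure indicator alone would mislead.** In the six orders, unexposed device strains sit at positions 1, 1, 1 and 2, mean 5/4 = 1.25. The eight exposed ones sit at 3, 4, 2, 4, 2, 3, 4 and 3, mean 25/8 ≈ 3.1. An indicator without strain order would mix gauge learning with ordinary practice or fatigue.

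**6. Why the crossover should stay.** A comparison of first strains only, 36 against 37 participants, would have about 30% power for 4 beats per minute at SD 12. Its detectable difference at 80% power is (1.960 + 0.842) × 12 × √(1/36 + 1/37) ≈ 7.9 beats per minute.

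**The case against.** The strongest reply is that the effect is hypothetical and bounded by the design. The device signals audibly at 40 mmHg and releases there, so earlier gauge exposure can raise pressure only in someone who would otherwise fall short despite that cue. The stopwatch and the instruction to stop apply to every strain, so a gauge adds little about how long to blow. Device-first participants also feel and hear the release point, so some learning may run the other way. Research question 3 asks for a comparison with a manometer, not for first-use performance, and the protocol envisages packaged instructions, clinical staff and patients with recurrent attacks, so a wholly unexposed user is only one relevant target.

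Most of this stands, and it limits the point. It removes duration as a main concern, confines the pressure effect mainly to shortfalls below 40 mmHg, and means the all-strains comparison should remain. It does not show that shortfalls are absent: whether the device reaches the required pressure is what the study sets out to learn. Nor does reverse learning help with the absolute level, since the excess s·a in the pooled device mean does not depend on b.

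A reader might also infer that the written model pools exposed and unexposed device pressures. It does not: it is stated for heart rate, and no pressure model is set out.

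**Conclusion.** The point holds as a conditional one about peak sustained pressure. At least half of device strains, and up to three quarters, follow a gauge-guided strain; that follows from the design. Whether this matters depends on gauge exposure helping later device strains, and, for the device-manometer difference, on its helping more than the reverse. Under those conditions the pooled device mean exceeds unexposed performance by 0.5 to 0.75 of the gain, and nothing planned would reveal it.

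It is tempting to conclude that carry-over is one-way, that the device's results will be inflated, or that the comparison is invalid. The documents do not support any of these. They contain no evidence that carry-over exists, no size and no direction; asymmetry is an inference from the unequal feedback. The sample size is unaffected.

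**What to change.** Keep the crossover, all four strains and the all-strains device versus manometer comparison for the third objective. Then:

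1. Pre-specify an additional estimate of device peak sustained pressure, as a mean with 95% CI, from device strains made before any manometer strain. Allow for participants who contribute two such strains. Always report it beside the all-strains result, and state that it addresses what the device delivers without prior gauge feedback. Because starting instrument is randomised, these participants are a random half.
2. Write down the pressure model, which the plan lacks, and include strain order (1 to 4). This adjusts for common practice or fatigue; it does not itself remove unequal carry-over, which is why item 1 is needed. Do not use an exposure indicator without strain order.
3. Do not let the basis of the conclusion depend on whether the two results differ. Fix the role of each in advance.

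The cost is a paragraph of analysis text. No extra participants or measurements are needed, since pressure is already recorded for every strain and each participant's order is allocated. The downside is the wider interval for the additional estimate, which comes from about half the participants.

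### The nadir heart rate is the single longest R-R interval of any kind, so a post-ectopic pause or an artefact gap can be scored as vagal slowing, possibly more often in the modified VM

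*Combined protocol and SAP*

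**What the plan says.** All measurement rules are in the protocol under Test Valsalva Manoeuvres.

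- **Baseline.** The pre-manoeuvre rate comes from "calculating the mean R-R interval of the 10 beats preceding each manoeuvre".
- **Nadir.** The lowest rate comes from "measuring and recording the longest R-R interval during and up to 15 seconds post manoeuvre", converted to beats per minute.
- **Outcome.** "The difference between the pre and post manoeuvre heart rate will indicate the degree of vagal tone".
- **Recording and reading.** A 3 lead monitor prints the strips. These are coded and read blind to technique, following a cited published study of vagal manoeuvre technique (reference 6).
- **Modified VM (items 3 and 4).** The strain is "followed by supine positioning and passive 45 degree leg lift immediately at the end of the strain for a further 15 seconds". Items 1 and 2, the supine VMs, describe no repositioning.
- **ECG abnormalities during testing.** The only rule concerns safety: a participant who "develops any significant or persistent ECG abnormalities, the individual will be immediately withdrawn from further testing".

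Figure 2 requires sinus rhythm and no ECG abnormality at entry. Statistical Analysis (Revised) names supine versus modified VM as the first contrast and bases the sample size on a 4 bpm difference.

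**The concern.** The two halves of the outcome tolerate a bad interval very differently. The baseline is a mean, so one bad interval is diluted. The nadir is a maximum over roughly 30 seconds of trace, so one bad interval can replace the whole measurement. The error at the nadir has one direction: a spurious long interval can only overstate slowing.

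The text does not prevent this. The entry criteria apply at screening, not to the test strips. An isolated premature beat or a single obscured QRS is neither significant nor persistent, so the withdrawal rule leaves it in. Blind reading does not remove a gap that is in the trace.

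Two consequences follow. Noise can enter all four manoeuvres. In addition, the back rest is lowered and the legs are raised just as the post-strain part of the window opens, and only in the modified VM. If movement obscures beats there, the mixed model cannot separate that artefact from a true effect of position. Whether posture increases vagal tone is the first of the Research Questions.

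**Working it through.** **1. The plan's own figure.** Inputs from Statistical Analysis (Revised): difference 4 bpm, SD of differences 12, 5% level, 80% power, paired t-test. Two-sided testing is assumed because the plan does not state it. By the noncentral t, n = 72 gives power 0.797 and n = 73 gives 0.802. The stated 73 is reproduced.

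**2. What one bad interval does.** Rate = 60,000 / R-R in ms. The rates below are assumptions; the documents give none.

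- At 70 bpm, R-R = 60,000/70 = 857 ms. The window (15 s strain plus 15 s after) holds about 30 × 70/60 = 35 beats.
- A premature beat at 60% coupling with a full compensatory pause: (2 − 0.6) × 857 = 1200 ms, read as 50 bpm. With no true slowing, the false drop is 20 bpm.
- An interval spanning one unreadable QRS: 2 × 857 = 1714 ms, read as 35 bpm. The false drop is 35 bpm.
- For comparison, one doubled interval among ten at baseline gives 70/1.1 = 63.6 bpm, an error of about 6 bpm.

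**3. The excess depends on where the bad interval falls.**

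- If the true nadir is 55 bpm, the same 1200 ms pause adds only 55 − 50 = 5 bpm.
- If the premature beat falls while the rate is 100 bpm, the pause is 1.4 × 600 = 840 ms. That is shorter than the 857 ms baseline interval and has no effect.
- A beat lost exactly at a nadir of 50 to 80 bpm halves the rate and adds 25 to 40 bpm.

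An excess of 10 to 30 bpm is used below as a working range.

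**4. Bias in the posture contrast.** If a share p of modified strips carries an average excess e, and supine strips carry none, bias = p × e:

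| Share of modified strips | e = 10 bpm | e = 30 bpm |
|---|---|---|
| 2% | 0.2 | 0.6 |
| 5% | 0.5 | 1.5 |
| 10% | 1.0 | 3.0 |

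Averaging over the two instruments does not reduce this if both modified VMs are affected alike. To produce the full 4 bpm from lost beats alone would need 4/40 = 10% to 4/25 = 16% of modified strips.

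**5. Which contrast is exposed.** Each instrument is used once in each posture, so the manometer versus device contrast is balanced for artefact due to repositioning. If artefact is equally common in both postures, the posture contrast gains noise but no bias.

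**The case against.** **The cited method may already deal with ectopics.** The protocol defers to a published method that was not available for this review. This stands as a limit: what can be said is that the rule as written out has no restriction. If the source has one, restating it is easy.

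**A person reads printed strips.** No automatic R-wave detector is described, and a reader may recognise a premature beat or refuse to measure across artefact. This makes a wholly missed beat less likely. Without a rule, though, such decisions are unrecorded and may vary between strips.

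**The population is healthy and screened.** Cardiovascular disease, regular medication (other than the oral contraceptive), recent caffeine, stimulants and alcohol are excluded. Frequency may be low; it is not known.

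**The difference between postures is not shown.** Nothing in the documents says that ectopics are commoner in either posture, and straining may disturb the trace in all four VMs. Only the repositioning is specific to the modified VM. The directional risk rests on movement alone.

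**A power loss is tempting to infer but not supported.** Adding noise to the paired SD as √(144 + 2p(1 − p)e²) gives, at p = 10% and e = 30, √306 = 17.5, and power falls from 80% to 49%. Two things undo this:

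- The SD of 12 comes from the same study whose measurement method is adopted, so it may already contain ordinary ectopic and reading noise.
- The planned mixed model uses two strips per posture if the interaction is dropped. Take a correlation of 0 to 0.5 between the two within-instrument differences (an assumption). The SD of their average is then 8.5 to 10.4, and power starts at 98% to 90%. In the same extreme case it is 78% to 69%.

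**Assumption checks might expose outliers.** The plan checks assumptions such as Normality, but it does not say what would then be done with an implausible nadir.

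**Conclusion.** The point holds as a gap in the measurement rule. As written, an interval that is not vagal slowing can be recorded as vagal slowing, and no other provision in the protocol prevents it. This can add noise in all four VMs, and movement could tilt the posture contrast towards the modified VM. Under the stated assumptions the bias is about 0.2 to 3 bpm against the 4 bpm design difference. The upper end needs one modified strip in ten to carry a 30 bpm excess that supine strips do not carry.

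A reader might go further and conclude that an ectopic pause will usually be the outcome, that a false benefit of the modified VM is to be expected, or that the study is underpowered. The documents support none of these. They give no artefact frequency and no nadir rates, they show no difference in ectopy between postures, and the size of any added noise is unknown. The right label is a cheap improvement, not a flaw that undermines the design.

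**What to change.** In the measurement paragraph, define the nadir as the longest fully readable interval between consecutive sinus beats. Then state:

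- An interval that follows a premature beat, or that spans an unreadable segment, is not eligible.
- A sinus pause ended by a late escape beat **is** kept. It may be the vagal effect itself, and a strict rule requiring a sinus beat at both ends would discard it.
- The same exclusions apply to the 10 baseline beats.
- The blinded reader makes each decision and records it with a flag on the data sheet.
- Exclusions and unreadable post-strain time are reported for each of the four manoeuvres.
- The unrestricted longest R-R interval is analysed as a sensitivity analysis.

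The cost is a few sentences and a data field or two; procedures and the sample size of 73 are unchanged. The downside is that a few intervals or strips are lost, possibly more in the modified VM, where movement coincides with the period just after the strain. Losing the true nadir there would bias against the modified VM. The report by manoeuvre and the sensitivity analysis would show whether that has happened.
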